## 9.0 Data and Safety Monitoring Plan

**This section is required when research involves more than Minimal Risk to subjects as defined in "HRP-001 SOP- Definitions."**

Minimal Risk is defined as the probability and magnitude of harm or discomfort anticipated in the research that are not greater in and of themselves than those ordinarily encountered in daily life or during the performance of routine physical or psychological examinations or tests. For research involving prisoners, Minimal Risk is the probability and magnitude of physical or psychological harm that is normally encountered in the daily lives, or in the routine medical, dental, or psychological examination of healthy persons.

**Please complete the sections below if the research involves more than minimal risk to subjects, otherwise indicate each section as not applicable.**

### 9.1 Periodic evaluation of data

Describe the plan to periodically evaluate the data collected regarding both harms and benefits to determine whether subjects remain safe.

Rare risk of reaction to Lumason – if any reactions occur, it will be known at the time of the exam and will be recorded/reported in REDCap. The PI will perform this study and will be aware of any reactions at that time. Additionally, this data will be reviewed monthly by the PI. Lumason will be administered per standard of care (FDA-approved), as used in the radiology department at Penn State Health. Contrast reactions will be managed per standard practice, as CT or MRI contrast reactions are handled.

### 9.2 Data that are reviewed

Describe the data that are reviewed, including safety data, untoward events, and efficacy data.

Patients are monitored for at least 15 minutes after injection of contrast, which is greater than how long the contrast bubbles remain intact in the circulation. Patients have a phone number on their consent form to call if there are any delayed concerns or reactions.

Monitoring and recording of any contrast reactions at the time of the ultrasound. Reported to the PI who will review monthly in aggregate to evaluate any trends. Standard of care TACE and follow-up CT/MRI will not be monitored for reactions.

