The CEUS will be performed and interpreted by a single radiologist, who is blinded to the CT/MRI, but not to the original tumor site and any prior images. A similarly blinded second radiologist will provide a second read of the CEUS to ensure accuracy at a later date. The same radiologists will be responsible for performing each task for research purposes and will both be members of the research study team. Results from the CEUS will not generate a formal report in the electronic medical record, but will be used only for the research study and entered into REDCAP. The CT or MRI will be interpreted formally by a clinical radiologist, and be dictated and entered into the electronic medical record as standard of practice, outside of the scope of this study. The patient will be administered a short survey about the modalities at the conclusion of their exams utilizing grading on a Likert scale.

### 7.2.3 Timepoint 2

Per standard clinical care, patients typically return for repeat imaging (CT/MRI) within 2-4 months following the first imaging visit. The decision for follow-up timing is not part of the study, but is decided upon by their clinical physicians. The results of these studies will be included in our data analysis, but no additional intervention will occur at this time.

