### 7.4 Test Article(s) (Study Drug(s) and/or Study Device(s))

#### 7.4.1 Description

Provide a brief description of all test articles (drugs (including any foods and dietary supplements), devices and/or biologics used in the research including the purpose of their use and their approval status with the Food and Drug Administration (FDA). Include information about the form of the drug product (e.g., tablets, capsules, liquid).

Contrast enhanced ultrasound utilizes standard ultrasound units with a contrast software package included on the machine. The test utilizes Lumason (Bracco), which comes in a sterile vial as a powder. It is reconstituted at the time of use with sterile saline (provided in the Lumason package). Each kit provides the equivalent of two liver doses (2.4 mL each). The reconstituted liquid Lumason is then injected intravenously, followed by a flush with sterile saline (5-10 mL saline after each Lumason dose). Lumason is FDA approved for liver lesion evaluation in adults, which is what this study is evaluating (specifically, liver lesions in patients with hepatocellular carcinoma after treatment). After TACE treatment, the liver lesion may shrink, but does not entirely disappear, so contrast ultrasound will be evaluating the residual lesion that is left – is there residual viable tumor left, or not.

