#### Lumason Risk

- **Serious Cardiopulmonary Reactions:** Serious cardiopulmonary reactions, including fatalities have occurred uncommonly during or shortly following administration of ultrasound contrast agents, including Lumason. These reactions typically occurred within 30 minutes of administration. The risk for these reactions may be increased among patients with unstable cardiopulmonary conditions (acute myocardial infarction, acute coronary artery syndromes, worsening or unstable congestive heart failure, or serious ventricular arrhythmias).
- **Ventricular Arrhythmia Related to High Mechanical Index**
- **Hypersensitivity Reactions:** There is a very small risk of allergic reaction to Lumason, the ultrasound contrast material
- **Systemic Embolization:** When administering Lumason to patients with cardiac shunt, microspheres can bypass filtering by the lung and enter the arterial circulation.
- **Risks of Lumason injection:** The discomfort associated with injecting Lumason is a slight pinch or pin prick when the sterile needle enters the skin. The risks include mild discomfort and/or a black and blue mark at the site of puncture. Less common risks include a small blood clot, infection or bleeding at the puncture site, and on rare occasions fainting during the procedure.

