#### Other Risks

- Discomfort includes the extra time required to perform the CEUS and to fill out the survey (estimated 30-45 minutes). Subjects are free to skip any questions that they prefer not to answer.
- Loss of confidentiality.

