### 11.2 Potential Benefits to Others

Include benefits to society or others.

If CEUS is shown to be non-inferior to CT/MRI, there would be several different benefits to future patients (and potentially the subject themselves, in follow-up) –

This study has the potential to specifically affect patients with cirrhosis or other liver diseases who have been diagnosed and treated for HCC, often used as a bridge to transplantation. Four phase CT and contrast enhanced MRI are the standard methods for establishing the success of TACE treatment by looking for residual disease and for new tumor, but may be contraindicated or not feasible in certain patients. CEUS has a safer overall risk profile and is also significantly less expensive than CT or MRI. Contrast reactions are rare in CEUS, the exam has less contraindications than CT or MRI. Additionally, multiple separate doses can be administered in CEUS to get a second or better look at an area of concern in the liver.

Intrinsically, ultrasound has high spatial resolution and has a potential for identifying residual or recurrent tumor at the same rates and potentially even earlier than a CT scan can, where ethiodol can obscure subtle signs of residual tumor (23). This would ensure that HCC patients are triaged appropriately and potentially decreases morbidity with a safe, accurate, and less expensive bridge to liver transplantation.

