## 15.0 Resources Available

### 15.1 Facilities and locations

Identify and describe the facilities, sites and locations where recruitment and study procedures will be performed.

If research will be conducted outside the United States, describe site-specific regulations or customs affecting the research, and describe the process for obtaining local ethical review. Also, describe the principal investigator's experience conducting research at these locations and familiarity with local culture.

Subjects will be identified and enrolled during the clinician office visit, if seen by a sub investigator or at the time of TACE in the CVIR suite.

Their follow-up CT/MRI and CEUS will be performed at either the main hospital or the East Campus location on the Penn State Health Hershey main campus grounds, due to convenience and privacy of the patient – CT/MRI and Ultrasound will be completed at the same location (in adjacent rooms/same hallway). Patient will not be required to leave the area to have all of the tests done.

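### The guaranteed 15 minutes of observation after Lumason covers only half of the 30-minute window in which the protocol says serious cardiopulmonary reactions typically occur

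*Combined protocol and SAP*

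**What the plan says.** Section 9.2 sets the observation rule and gives its reason in one sentence: "Patients are monitored for at least 15 minutes after injection of contrast, which is greater than how long the contrast bubbles remain intact". For anything later, it relies on a telephone number printed on the consent form.

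Section 10.0 (Lumason Risk) describes serious cardiopulmonary reactions, "including fatalities have occurred uncommonly during or shortly following administration of ultrasound contrast agents, including Lumason", and adds: "These reactions typically occurred within 30 minutes of administration".

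Other sections bear on how long a patient stays on site and which injection starts the clock:

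- Section 7.2.2 puts the CT or MRI and the CEUS at one visit but does not give their order. It then says: "The patient will be administered a short survey about the modalities at the conclusion of their exams".
- Section 15.1 says "CT/MRI and Ultrasound will be completed at the same location (in adjacent rooms/same hallway", and Section 13.0 pays the gift card only after both exams and the survey.
- Section 10.0 (Other Risks) tells patients to expect "extra time required to perform the CEUS and to fill out the survey (estimated 30-45 minutes".
- Section 7.4.1 says "Each kit provides the equivalent of two liver doses (2.4 mL each", and Section 11.2 notes that "multiple separate doses can be administered in CEUS to get a second or better look".
- Section 9.3 assumes that reactions are recognised during the exam and recorded on the case report form and in REDCap.

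**The concern.** The reason given for 15 minutes is a property of the contrast agent: how long the bubbles last. The hazard in Section 10.0 is a clinical event with its own stated timing, and that timing runs to twice the guaranteed observation. Nothing in the protocol links the two or explains why 15 minutes is enough.

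The patient bears the consequence. An acute cardiopulmonary event at minute 20, after the patient has left observation, is the situation in which a telephone number helps least. The CEUS is done only for research, Section 11.1 offers no direct benefit at the time of the study, and Section 14.2 leaves the cost of treating an injury with the patient or insurer. The study creates the exposure, so its own observation should cover the risk window it states.

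There are two smaller gaps. Section 9.2 does not say which injection starts the clock if a second dose is given. It also invites telephone reports of delayed reactions, but Section 9.3 gives no route for those reports into the study data.

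**Working it through.** There is no sample-size, power or error-rate figure to reproduce. The check compares stated times and then prices the change.

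**Inputs**

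| Input | Value | Source |
|---|---|---|
| Guaranteed observation | 15 minutes (minimum) | Section 9.2 |
| Typical onset window for serious cardiopulmonary reactions | 30 minutes | Section 10.0, Lumason Risk |
| Planned enrolment | 34 | Sections 8.1 and 8.2 |
| Added visit time for CEUS and survey | 30-45 minutes | Section 10.0, Other Risks |

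**Size of the gap.** Window minus guaranteed observation: 30 - 15 = 15 minutes. The guarantee covers 15/30 = half of the window in minutes. That is not half of the risk. Section 10.0 places these events during or soon after the injection, so they may cluster early, and no onset-time distribution is given. The proportion between minutes 15 and 30 therefore cannot be computed.

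**Does anything else guarantee minutes 15 to 30?**

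1. If CEUS comes first, the CT or MRI follows and the patient probably stays on site through minute 30. That time is not defined as observation for Lumason reactions. Section 9.2 also says the standard-of-care follow-up CT/MRI is not monitored for reactions. Even if this means reactions to the CT or MRI contrast, it promises no Lumason monitoring during the scan.
2. If CEUS comes last, only the short survey has to follow. Its length is not stated separately.
3. The order is not fixed in Section 7.1 or 7.2, so the second case is allowed.

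No section closes the gap for every patient.

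**Cost ceiling.** If no survey or CT/MRI time can be counted, the extra time is 34 x 15 = 510 minutes, or 510/60 = 8.5 hours over the whole study.

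**Effect on the time estimate given to patients.** The protocol does not say whether its 30-45 minutes includes the present observation, so both readings are assumptions:

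- If it is included, the time rises from 30-45 to at most 45-60 minutes (adding 15).
- If it is not included, the time is now 45-60 minutes (30-45 plus 15) and becomes at most 60-75 (30-45 plus 30).

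**The case against.** The strongest reply is that nothing here is contradictory. Section 9.2 sets a floor, Section 10.0 gives a typical outer bound for uncommon events, and the choice of floor is a matter of judgement. The documents do not say that 30 minutes of observation is required or customary. Sections 7.4.2, 7.4.6 and 9.1 place Lumason use within the FDA label and departmental practice, and whether 15 minutes departs from either cannot be checked from the documents. Exclusion criterion 4 in Section 3.2 removes patients with unstable cardiopulmonary conditions, the group for whom Section 10.0 says risk may be increased. Reactions are managed as CT or MRI contrast reactions are. The exams share a location, a survey follows, payment waits for all three, and 34 patients is a small number.

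Much of this stands. The risk is low, the harm cannot be quantified, and many patients will in practice be nearby at minute 30. No breach of a label or regulation is shown. But these points lower the probability of harm without supplying observation. Section 10.0 says risk may be higher in unstable patients, not that it is confined to them. The references to label and usual practice give no observation time, and time in the building is not time under observation.

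The objection also has force on the smaller points. Section 7.4.2 gives a 2.4 mL dose and does not require a second; Section 11.2 speaks of CEUS in general; and an injection-based clock can be read as starting when injection is complete. Telephone calls appear in Section 9.3 only as an example in the template prompt. Section 9.4 records adverse events at imaging time points, and Section 18.1 sends unexpected, probably related harms to the IRB. These two points are clarifications and do not carry the concern.

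**Conclusion.** The concern holds. Guaranteed observation ends 15 minutes before the end of the onset window the protocol itself states for serious cardiopulmonary reactions, and the reason given for the shorter time does not address that window. A patient managed exactly as written may leave study observation inside it.

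The conclusion rests on the two stated times and on the exam order being unspecified. It does not rest on any assumed onset distribution, and no number of missed reactions is claimed. Endpoints and estimates are untouched. This is an inexpensive safety improvement that should be made.

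**What to change.** In Section 9.2, set a minimum of 30 minutes of observation counted from the last Lumason dose, and give the Section 10.0 onset window as the reason in place of bubble lifetime. State that survey or CT/MRI time at the same visit counts only if staff can observe the patient for Lumason reactions. Revise the time estimate in Section 10.0 (Other Risks) if it changes.

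As a minor addition, state in Section 9.3 that reactions reported after the exam, including by telephone, are entered on the case report form and in REDCap.

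The cost is wording in two sections, one case report form field, and up to about 15 more minutes for some patients, within the ceiling worked out above. Part of that time can be absorbed by the survey or CT/MRI, and no procedure is added.

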#### 9.3 Method of collection of safety information

Describe the method by which the safety information will be collected (e.g., with case report forms, at study visits, by telephone calls and with subjects).

As part of the case report form – reactions will be known at the time of the exam. It will be reported on the form, and recorded in REDCap. The PI will review these monthly in aggregate to evaluate for any trends.

#### 9.4 Frequency of data collection

Describe the frequency of data collection, including when safety data collection starts.

Adverse events will be recorded at each imaging time point.

#### 9.5 Individuals reviewing the data

Identify the individuals who will review the data. The plan might include establishing a data and safety monitoring committee and a plan for reporting data monitoring committee findings to the IRB and the sponsor.

PI – [name].

#### 9.6 Frequency of review of cumulative data

Describe the frequency or periodicity of review of cumulative data.

Monthly

#### 9.7 Statistical tests

Describe the statistical tests for analyzing the safety data to determine whether harms are occurring.

Large scale studies have been reported in the use of Lumason, including in patients with chronic liver disease have very low rates of reaction (<1%) and very rare severe reactions. Data will be reviewed monthly and if any reactions occur in that timeframe, the set will be given to the statistician to determine if rates are the same or above reported rates.

#### 9.8 Suspension of research

Describe any conditions that trigger an immediate suspension of research.

Higher reaction rates (allergic) than reported studies.

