**Table 1. Adverse Reactions in Adult Patients\***  
n = 6856

|   |           |
|---|-----------|
| Number (%) of Patients with Adverse Reactions | 340 (5%)  |
| Headache                                      | 65 (1%)   |
| Nausea  | 37 (0.5%) |
| Dysgeusia                                     | 29 (0.4%) |
| Injection site pain                           | 23 (0.3%) |
| Feeling Hot                                   | 18 (0.3%) |
| Chest discomfort                              | 17 (0.2%) |
| Chest pain                                    | 12 (0.2%) |
| Dizziness                                     | 11 (0.2%) |
| Injection Site Warmth                         | 11 (0     |

\*occurring in at least 0.2% of patients

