## 11.0 Potential Benefits to Subjects and Others

### 11.1 Potential Benefits to Subjects

Describe the potential benefits that individual subjects may experience from taking part in the research. If there is no direct benefit to subjects, indicate as such. Compensation is not considered a benefit. Compensation should be addressed in section 13.0.

There is no direct benefit to the patient at the time of their study.

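### Section 9.8 suspends the study only on a raised allergic reaction rate; no section states an immediate pause after a single serious or fatal Lumason reaction

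*Combined protocol and SAP*

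**What the plan says.** Section 9.8 asks which conditions trigger an immediate suspension. The whole answer is "Higher reaction rates (allergic) than reported studies".

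Section 9.7 supplies the comparison. It cites large studies with "very low rates of reaction (<1%) and very rare severe reactions". Data are reviewed monthly, and "if any reactions occur in that timeframe, the set will be given to the statistician", who judges whether rates match or exceed those reported. No test, threshold or single-event rule is given.

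Section 10.0, under Lumason Risk, puts the risks in separate bullets. One reads "Serious cardiopulmonary reactions, including fatalities have occurred uncommonly during or shortly following administration of ultrasound contrast agents, including Lumason". Ventricular arrhythmia and systemic embolization have their own bullets. Hypersensitivity is another: "There is a very small risk of allergic reaction to Lumason, the ultrasound contrast material".

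On awareness, section 9.1 says "The PI will perform this study and will be aware of any reactions at that time". On benefit, section 11.1 says "There is no direct benefit to the patient at the time of their study".

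**The concern.** The suspension rule names the allergic category, while the gravest risks that the protocol itself describes sit in other categories. Taken literally, a non-allergic cardiopulmonary death shortly after injection meets no stated suspension condition. Even for an allergic event, the condition is a rate judged through a monthly cycle, which is not an immediate response to one event.

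At stake is whether research injections stop while such an event is reviewed. The CEUS is done for research only, gives the subject no direct benefit, and generates no formal report in the medical record (section 7.2.2). A pause would therefore withhold no care, while continuing by default would expose further subjects before anyone has looked at the event.

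**Working it through.** The protocol gives no figure for a stopping rule, so there is nothing to reproduce. The main check is a reading of every section that could contain a pause.

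**Sections side by side**

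| Section | What it provides | Pause for one serious event? |
|---|---|---|
| 9.1 | The PI performs the exam and knows of reactions at once; they are managed by standard practice | No |
| 9.2, 9.3, 9.6 | Reactions recorded; monthly aggregate review by the PI | No |
| 9.5 | The PI is the only reviewer named | No |
| 9.7 | Monthly data; the statistician compares with reported rates | No |
| 9.8 | Suspension if the allergic rate is above reported rates | No; a rate condition |
| 10.0 | Serious and fatal cardiopulmonary reactions and arrhythmia listed apart from hypersensitivity | No |
| 17.6 | Six-monthly team meetings covering significant toxicities and reportable events; minutes to the DSMC | No |
| 18.1 | IRB report of harms that are both unexpected and probably related | No; reporting only |

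**Two readings of section 9.8**

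- *Strict.* The bracketed word limits the rule to allergic reactions. Serious non-allergic reactions are outside it.
- *Broad.* The bracketed word is a loose label for contrast reactions, which fits section 9.7, where any reaction goes to the statistician. One event among at most 34 injected subjects is a rate of at least 1/34 = 2.9%, numerically above the <1% cited. With no test or threshold set, one severe event could be judged to meet the rule, but only when the section 9.7 comparison is made.

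Neither reading yields a stated immediate pause.

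**How often an added rule would apply**

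Inputs: N = 34 (section 8.1). Section 9.7 calls severe reactions very rare but gives no number, so p = 0.01% to 0.1% per subject is an assumption.

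P(at least one) = 1 − (1 − p)^34

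- p = 0.0001: 1 − 0.9999^34 = 0.0034, or 0.3%
- p = 0.001: 1 − 0.999^34 = 0.0334, or 3.3%

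These cover severe reactions of any kind, so the chance for non-allergic ones is no higher. Subjects whose lesion is not visible on grayscale receive no contrast (section 3.3.1), so 34 is an upper bound on the number injected at the planned size.

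**The case against.** The best case against is that this is largely preference in a single-site pilot of 34. Lumason is FDA-approved for liver lesions and is given at the standard liver dose (sections 7.4.1 and 7.4.2). Unstable cardiopulmonary conditions are excluded (section 3.2). The PI is in the room, so no information has to travel before injections are halted, and the PI and the IRB can stop the study at their discretion. Section 17.6 reviews significant toxicities, not only allergic ones. On the assumed rates there is a 96.7% to 99.7% chance that a single-event rule would never be used. All of this stands, and it limits the weight of the point.

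It does not supply the missing rule. Discretion is not a stated condition, and the section 17.6 meetings are six-monthly. Section 18.1 requires a harm to be unexpected, and a reaction already listed in section 10.0 might be judged expected.

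Two stronger readings are tempting and are not supported.

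- A reader might infer that a rate rule cannot respond to one fatal event: at a true rate of 1%, the chance of at least one reaction in 34 is 1 − 0.99^34 = 28.9%, so one reaction looks unremarkable. That uses the benchmark for all reactions. Section 9.7 sets severe reactions apart as very rare, and at the assumed 0.01% to 0.1% the chance of one or more is only 0.3% to 3.3%, so one severe event would itself point to an excess.
- A reader might infer that injections would in practice continue unexamined after a death. The documents do not show that, given the PI's immediate knowledge and the oversight above. They show only that no pause is written down.

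**Conclusion.** The point holds as a gap in the stated rule. The only immediate-suspension condition in section 9.8 is an allergic reaction rate, assessed through the monthly process in section 9.7. It does not expressly cover the non-allergic serious or fatal reactions in section 10.0, and no section requires an immediate pause after one serious event.

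This is a cheap safety improvement, not a serious defect. The textual finding rests on no assumption. The 0.3% to 3.3% does: it depends on the assumed severe rate, on 34 subjects, and on independence between subjects. Section 8.2 mentions adding patients as funding allows, which would raise the chance somewhat.

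**What to change.** Keep the existing allergic-rate trigger and add one or two sentences to section 9.8, for example: *Any single serious, life-threatening or fatal reaction possibly related to Lumason, whether or not allergic and whether or not listed in section 10, pauses further CEUS injections pending review. The IRB and the DSMC are notified promptly.*

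The possibly-related standard and the listed-or-not clause matter because section 18.1 alone may not reach a known risk. No new body is needed: the protocol already refers to the IRB and, in section 17.6, to a DSMC. The cost is a short text change and, if the rare event occurs, a possible brief halt in CEUS exams and some extra reporting. Standard-of-care CT/MRI would be unaffected.
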